**Table 4 Local laboratory parameters**

Mandatory at Screening and the EOT visit; optional at active treatment visits and the TOC visit:		
Haematology	Blood chemistry	Urine analysis (dipstick)
Haematocrit	ALT	Blood
Red blood cell count	AST	Glucose
White blood cell count	Bilirubin (total)	Ketones
Absolute and immature neutrophils	Creatinine	Leukocytes
Platelets	Sodium	Nitrite
	Potassium	pH
	Bicarbonate	Protein

Optional at Screening and active treatment visits:	Blood chemistry
	Anion gap
	C-reactive protein
	Procalcitonin
	IL-6

EOT=end-of-treatment; ALT=alanine aminotransferase; AST=aspartate aminotransferase; TOC= test-of-cure.

Note: Optional blood tests may be performed at the discretion of the Investigator in accordance with local standard of care, taking into consideration the maximum allowable blood draw volumes.

See the Laboratory Manual for blood volumes to be drawn from each patient for the local laboratory tests and for PK sampling. The combined volume of blood samples taken for study purposes or as part of standard of care must not exceed the limit specified in the Laboratory Manual. Any deviations from this must be clinically justified.

### 5.5.5 Pregnancy testing

Not applicable.

## 5.6 Efficacy assessments

### 5.6.1 Overall clinical outcome

At the EOT and TOC visits, the Investigator must assess the overall clinical outcome as:

- ***Clinical cure***
  - Signs and symptoms of LOS improved or normalised to an extent that no further antibacterial therapy is required
- ***Clinical failure***
  - Discontinuation of study treatment and requirement for non-study antibacterial therapy because of:
    - Insufficient therapeutic effect associated with study treatment, including persistence or worsening of signs and symptoms of LOS
    - AE related to the study treatment
  - Death attributable to LOS

- ***Unevaluable***

- Study data not available for evaluation of efficacy for any reason, including:
  - Lost to follow-up
  - Received < 48 hours of study treatment
  - Concomitant treatment with a systemic antibacterial administered for a reason other than LOS, which is active against the isolated LOS pathogen, or in the absence of microbiological evaluation, is active against common LOS pathogens
  - Diagnosis of any of the following conditions after enrollment in the study and discontinuation of study treatment: ventilator-associated pneumonia, meningitis, brain abscess, osteomyelitis, infective endocarditis, or necrotising enterocolitis
  - Death in which LOS is clearly non-contributory
  - Absence of clinical assessment for any reason

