## 3 STUDY DESIGN

This is a multicenter, open-label, single-arm, multiple-dose study of IV ceftobiprole in term and pre-term neonates and infants up to 3 months of age with LOS. At least eight patients, at least two term (gestational age  $\geq 37$  weeks) and at least six pre-term (gestational age  $\geq 24$  to 36 weeks), with post-natal age ranging from  $\geq 3$  days to  $\leq 3$  months will be enrolled at approximately ten sites in Europe and USA, with additional sites and locations possible.

Study therapy consists of IV ceftobiprole medocaril for 3–10 days, which may be extended to 14 days if considered clinically necessary by the Investigator. Ceftobiprole may be combined with ampicillin and/or an aminoglycoside based on the Investigator's judgement, local standard of care, and/or isolated or presumed pathogens. If added, the treatment duration of ampicillin and/or an aminoglycoside is at the discretion of the Investigator.

Each patient is expected to complete the study in approximately 5–7 weeks, including screening, an estimated treatment duration of 3–10 days with possible extension up to 14 days, end-of-treatment (EOT) visit, TOC visit 7–14 days after last ceftobiprole dose, and a last follow-up (LFU) visit 28–35 days after last ceftobiprole dose.

[figure not shown]
Safety assessments will be done throughout the study. Specimens for microbiological assessment will be obtained as clinically indicated in accordance with local standard of care. Blood samples for PK analysis will be collected on Day 3. Efficacy outcomes will be assessed at the EOT, TOC, and LFU visits.

The DSMB will review data on a regular basis to assess the safety of all patients enrolled in this study (see Section 3.4).

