## 3.3 Treatment plan

### 3.3.1 Dose modifications

The intended dose of IV ceftobiprole may not be modified. As patients with moderate or severe renal impairment will be excluded, no need for dose adjustment is expected. Study drug may be discontinued at any time at the Investigator's discretion (see Section 4.4). If a patient's estimated glomerular filtration rate (using the Schwartz formula or other applicable formula) decreases to less than two-thirds of normal for the applicable age group, or urinary output decreases to  $< 0.5$  mL/kg/h (measured over at least 8 hours) during study drug treatment, ceftobiprole administration should be stopped and the patient should be switched to standard of care treatment. If continuation of ceftobiprole is considered necessary by the Investigator based on an individual medical benefit-risk assessment for a patient, then the implementation of real-time plasma level assessments of ceftobiprole is recommended.

If added, any dose modification for ampicillin and/or an aminoglycoside is at the discretion of the Investigator in accordance with local standard of care; aminoglycoside dose modification may be based on renal function or therapeutic drug monitoring.

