#### **4.4 Patient withdrawal**

Parents or LARs may voluntarily withdraw consent for the patient's participation in the study at any time for any reason. The Investigator may also withdraw a patient from the study for reasons which may include adverse reactions (including but not limited to allergic-type reactions, infusion site reactions, or clinically relevant changes in vital signs), apparent infant distress, or at the request of the parent or the LAR.

If patients are withdrawn, the date of withdrawal and the reason for withdrawal must be recorded in the electronic case report form (eCRF).

If a patient who has received at least one dose of study drug discontinues treatment at any time for reasons other than withdrawal of consent, every effort must be made to complete the EOT and LFU visits.

Reasons for discontinuation of study treatment must be recorded, and may include:

- Adverse event
- Abnormal laboratory value
- Abnormal test procedure result
- Intercurrent illness that prevents further administration of treatment
- Diagnosis of any of the following conditions after enrollment in the study: ventilator-associated pneumonia, meningitis, brain abscess, osteomyelitis, infective endocarditis, or necrotising enterocolitis
- Confirmation of reduced susceptibility to ceftobiprole of any pathogen isolated
- Death
- Withdrawal of consent
- Withdrawn from the study at the Investigator's discretion
- Protocol deviation/non-compliance
- Lost to follow-up
- Administrative reasons

The reasons for discontinuation of study treatment must be recorded in the eCRF.

For all patients who discontinue study treatment, AE monitoring must be continued up to and including the LFU visit. For patients who fail to return for the LFU visit, the

Investigator must make every effort to contact the parent(s) or LAR (by telephone or mail correspondence). The outcome of this contact must be documented by the Investigator and filed in the Investigator Site File (ISF).

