### 5.6.3 Microbiological outcome

The microbiological outcome categories at EOT and TOC are defined below. For a patient to have a favorable microbiological response, the outcome for each baseline pathogen must be eradicated or presumed eradicated. If the outcome for any pathogen is persistence or presumed persistence, the patient will be considered to have an unfavorable microbiological response.

Microbiological outcome is to be assessed at the EOT and TOC visits by the Investigator as follows

- ***Eradication***: Absence of baseline pathogen in follow-up cultures of source specimen
- ***Presumed eradication***: Absence of follow-up microbiological evaluation of source specimen, or unavailable microbiological results, for a patient with a valid baseline pathogen who was assessed as a clinical cure
- ***Persistence***: Continued presence of a baseline pathogen in follow-up cultures of any source specimen
- ***Presumed persistence***: Absence of follow-up microbiological evaluation of source specimen or unavailable microbiological results for a patient with a valid baseline pathogen and assessed as a clinical failure
- ***Unevaluable***: No valid pathogen identified at baseline, or no follow-up microbiological evaluation of source specimen obtained in a patient with clinical outcome assessed as unevaluable
- ***Relapse***: Baseline pathogen detected again in follow-up microbiological evaluation of any source specimen obtained between the TOC and LFU visits after documented eradication or presumed eradication at the TOC visit (note: this applies only to the microbiological outcome assessment at the LFU visit)

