## 8 EFFICACY ANALYSIS

### 8.1 Overall clinical outcome

Overall clinical outcome is to be assessed at the EOT and TOC visits by the Investigator as ‘Clinical cure’, ‘Clinical failure’, or ‘Unevaluable’ (see protocol Section 5.6.1 for details). Clinical cure rate and reasons for failure or unavailability of data will be summarized in a table for the ITT and CE populations.

### 8.2 All-cause mortality through Day 28

Vital status is to be assessed at the LFU visit, in person or by telephone contact. Patients will be considered to have died at Day 28 if they meet all the following criteria:

- A death is reported on the eCRF
- The study day for death is  $\leq 28$ .

The ACM at Day 28 will be summarized in a table for the ITT population.

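### At TOC, ITT clinical cure and mITT eradication can credit ceftobiprole with the effect of a replacement antibiotic, because some switches for LOS fall under no failure or unevaluable item

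*Protocol*

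**What the plan says.** **Clinical outcome (Protocol 5.6.1).** Cure is: "Signs and symptoms of LOS improved or normalised to an extent that no further antibacterial therapy is required". Failure, apart from death attributable to LOS, is: "Discontinuation of study treatment and requirement for non-study antibacterial therapy because of" one of two reasons. The first is "Insufficient therapeutic effect associated with study treatment, including persistence or worsening of signs and symptoms of LOS"; the second is an AE related to study treatment. Unevaluable means that study data are not available for evaluating efficacy. Its listed items include under 48 hours of treatment, a systemic antibacterial given for something other than LOS, and stopping after one of six named new diagnoses.

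**Routes off ceftobiprole.** If renal function or urine output falls below the stated limits, Protocol 3.3.1 says "ceftobiprole administration should be stopped and the patient should be switched to standard of care treatment", while allowing continuation on an individual benefit-risk assessment. Protocol 4.4 lists further reasons for stopping, among them AEs of any causality, Investigator discretion and "Confirmation of reduced susceptibility to ceftobiprole of any pathogen isolated".

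**Microbiology (Protocol 5.6.3).** Eradication is "Absence of baseline pathogen in follow-up cultures of source specimen". Presumed eradication applies when there is no follow-up result and the infant is rated a clinical cure. SAP 8.3 counts both as success.

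**Analysis.** SAP 8.1 refers back to 5.6.1 and adds: "Clinical cure rate and reasons for failure or unavailability of data will be summarized in a table for the ITT and CE populations". TOC is 7–14 days after the last ceftobiprole dose. Cure is reported in ITT and CE, eradication in mITT and ME.

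**The concern.** Cure and eradication at TOC are secondary efficacy endpoints of a single-arm study, so no control group would show how much of a rate is owed to other drugs. The cure wording describes a state and is silent on how it was reached. The 7–14 days between the last dose and TOC leave time for a replacement drug to act. An infant taken off ceftobiprole because the pathogen had reduced susceptibility, and then treated successfully with something else, could appear in the ITT table as a cure and in the mITT table as an eradication. The SAP 8.1 table gives reasons for failure or missing data only, so the switch behind a cure would not show there.

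**Working it through.** The documents give no expected cure rate, power or switch frequency, so there is no planned figure to reproduce beyond 2 term + 6 pre-term = 8 (Protocol 8.3). The check is a trace of each route through the definitions, followed by simple arithmetic.

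**Step 1. Clinical rating at TOC.** Take an infant with at least 48 hours of ceftobiprole, switched to a non-study systemic antibacterial for LOS, and well by TOC.

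| Reason for switch | Failure item met? | Listed unevaluable item met? | Cure wording met? |
|---|---|---|---|
| Insufficient effect | Yes | No | Yes |
| Related AE | Yes | No | Yes |
| Listed new diagnosis | No | Yes | Yes |
| Renal decline not judged a related AE (3.3.1) | No | No | Yes |
| Reduced susceptibility without clinical non-response (4.4) | No | No | Yes |
| Unrelated AE (4.4) | No | No | Yes |
| Investigator discretion (4.4) | No | No | Yes |

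In the last four rows cure is the only category whose wording fits. In the first two, failure and cure wording are both met at TOC. Neither document says that failure takes precedence or that an EOT failure carries forward.

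**Step 2. Microbiological rating at TOC.** The eradication definition mentions neither therapy nor clinical outcome. A negative culture after a switch for any reason therefore qualifies, even in a clinical failure. Without a culture, an infant from the last four rows who is rated cure becomes a presumed eradication.

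**Step 3. Which analyses are exposed.**
- *ITT and mITT:* neither population has an antibiotic condition, so both are exposed.
- *CE:* Protocol 8.2.2 excludes concomitant systemic non-study antibiotics, and SAP 7.1 counts drugs started after the first dose as concomitant. The switched infant is out.
- *ME:* it is a subset of CE, so the infant is out here too.
- *EOT cure:* EOT is within 24 hours of the last dose. An infant being switched still needs antibacterials and does not meet cure.
- *Missing-data rule (Protocol 8.4.5):* it makes unknown or unreported responses non-responses. Here a response is reported, so it does not apply.

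**Step 4. Size.** Shift in percentage points = 100 × k/n, where k is the number of such infants rated a success and n the denominator.
- ITT, n = 8: k = 1 gives 100 × 1/8 = 12.5; k = 2 gives 25.0. For example, 5/8 = 62.5% becomes 6/8 = 75.0%.
- By the SAP's subgroups, k = 1: pre-term 1/6 = 16.7; term 1/2 = 50.0.
- The mITT size is not given. If it were 6, 4 or 2 (assumption), one infant moves eradication by 16.7, 25.0 or 50.0 points.

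The chance of at least one such switch among eight is 1 − (1 − p)^8. With p assumed at 5%, 10%, 20% or 30%, it is 34%, 57%, 83% or 94%. These values of p are illustrative; the documents support none of them.

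**The case against.** The definitions already catch much of this. Switches for insufficient effect or a related AE have a failure item, and early stops and the named new diagnoses are unevaluable. The renal route will often end as a failure, because renal failure is an AE of special interest and the criteria for possibly related in Protocol 7.3.2 are wide. Known resistance is excluded at entry. The unevaluable list is open-ended, so an Investigator might use it for a confounded case. CE and ME give analyses free of these infants, efficacy is descriptive, and with about eight infants the listings would show each switch.

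Most of this stands and limits the point to ITT cure and mITT eradication at TOC. It does not remove the gap. The unevaluable category is framed around data being unavailable, and here they are available; leaving the choice to the Investigator in an open-label study makes the rate depend on individual reading. Listings allow a reader to find the case but do not correct the tabulated rate.

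A reader might infer three stronger claims that the documents do not support.
- *Every infant rescued by another drug counts as a cure, in every TOC analysis.* The failure and unevaluable items and the CE and ME exclusions contradict this.
- *Infants who finish on ampicillin or an aminoglycoside alone are misclassified.* These are permitted partner drugs: "If added, the treatment duration of ampicillin and/or an aminoglycoside is at the discretion of the Investigator". Such infants may stay in CE, since non-study is not defined, but counting their outcome is a defensible description of the regimen.
- *All the outcome rules favour the drug.* Related-AE switches count as failures even if the infant was improving, and unknown responses count as non-response.

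**Conclusion.** The concern holds in limited form. For ITT cure at TOC, it applies after at least 48 hours of ceftobiprole and a switch to non-study systemic antibacterials for LOS, for a reason other than insufficient effect, a related AE or a listed new diagnosis. For mITT eradication at TOC, it applies to a negative culture after a switch for any reason, and to eradication presumed from a cure reached on the replacement. The missing precedence and carry-forward rule adds an ambiguity for infants switched for lack of effect or a related AE. Where this gap operates, it raises the reported success rate.

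Each case is worth 12.5 points of ITT cure, assuming the planned eight infants. Whether there will be any case is unknown. This is a stated rule that gives a wrong result for identifiable infants. It affects secondary descriptive endpoints and leaves the primary safety objective untouched.

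**What to change.** - **Protocol 5.6.1 / SAP 8.1:** state that clinical cure requires that no non-study systemic antibacterial was given for LOS between the first ceftobiprole dose and the visit. Count infants who received one as not cured in ITT, and tabulate the reason for the switch. State that a failure at EOT carries forward to TOC. Define non-study so that permitted ampicillin and aminoglycosides are clearly outside it.
- **Protocol 5.6.3 / SAP 8.3:** do not count as eradication any clearance first documented after a switch to non-study antibacterials, or presumed from a cure reached on them.
- **Partner drugs:** where permitted ampicillin or an aminoglycoside for LOS outlasted ceftobiprole, keep the Investigator's rating and show the number of such infants on a separate descriptive line.

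The cost is definition wording and a derivation. Protocol 5.2.2 already records start and stop times for ceftobiprole and the partner drugs, and Table 3 records concomitant medications through LFU. The derivation also needs the reason for each antibacterial. The documents do not say that the eCRF holds it, though 5.6.1 already requires the Investigator to judge it. Reported ITT cure and mITT eradication rates may be slightly lower. The change concerns outcome classification only and alters no treatment rule.

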#### **5.6.4 Relapse at LFU**

At the LFU visit, the Investigator must assess relapse as follows:

- Deterioration of the patient's clinical condition compared to the TOC visit, microbiological recurrence, or the requirement for additional antimicrobial therapy for LOS

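### The clinical outcome categories are neither exhaustive nor mutually exclusive: re-treatment for LOS between EOT and TOC meets no failure criterion and can be counted as cure, and failure before 48 hours carries two labels

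*Protocol*

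**What the plan says.** Protocol 5.6.1 requires a rating at two visits: "At the EOT and TOC visits, the Investigator must assess the overall clinical outcome as" cure, failure or unevaluable.

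- **Cure:** "Signs and symptoms of LOS improved or normalised to an extent that no further antibacterial therapy is required".
- **Failure, first criterion:** "Discontinuation of study treatment and requirement for non-study antibacterial therapy because of" lack of effect (including persisting or worsening LOS) or a related adverse event.
- **Failure, second criterion:** "Death attributable to LOS". Neither failure criterion states a minimum exposure.
- **Unevaluable:** "Study data not available for evaluation of efficacy for any reason, including" a list of situations. One of them, without exception, is "Received < 48 hours of study treatment".

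TOC falls 7–14 days after the last dose (Protocol 3). Relapse is a separate assessment made at LFU (Protocol 5.6.4): deterioration of the patient's "clinical condition compared to the TOC visit, microbiological recurrence, or the requirement for additional antimicrobial therapy for LOS". Protocol 5.6.3 restricts microbiological relapse to the LFU assessment. It also makes the microbiological outcome depend on the clinical rating when no follow-up culture result exists. A clinical cure then gives presumed eradication. Presumed persistence applies "for a patient with a valid baseline pathogen and assessed as a clinical failure". An unevaluable clinical rating gives unevaluable.

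SAP 8.1 refers back to Protocol 5.6.1 and adds no derivation or precedence rule.

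**The concern.** TOC is the visit that should show whether a response seen at the end of treatment held once the drug was stopped. The failure definition does not describe the event that TOC is meant to detect, namely LOS returning after a completed course. Protocol version 5.0 reduced the expected minimum treatment duration from 7 to 3 days, so short completed courses are within plan.

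Two things are at stake. First, an infant re-treated for LOS and well again by TOC can be reported as a cure. With about eight infants, one such rating visibly changes the cure rate. Second, infants who fail earliest can be rated either way at the investigator's discretion, so two sites could classify the same course differently.

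**Working it through.** The plan states no figure for this point, so the check is mainly logical. The one number that can be reproduced is the 48-hour rule: 48/12 = 4 infusions every 12 hours and 48/8 = 6 every 8 hours, which agrees with Protocol 8.2.2.

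**Path A: course completed, antibacterials needed again for LOS before TOC.**

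1. *Failure?* No. There was no LOS death, and a completed course is not a discontinuation. Completion is not among the discontinuation reasons in Protocol 4.4.
2. *Relapse?* Not at TOC. Relapse is an LFU assessment.
3. *Unevaluable?* Not by its lead-in, because the recurrence and its treatment are recorded data. The listed item on other systemic antibacterials covers only those given for a reason other than LOS.
4. *Cure?* Not while re-treatment is still needed; no category then fits. If re-treatment has ended and the infant is well at TOC, no further therapy is required and the cure wording is met.

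Step 4 can happen within the TOC window. Let re-treatment start *d* days after the last dose and last *r* days, with TOC on day *t* (7 to 14). It is finished by TOC if *d* + *r* ≤ *t*. The documents give no value for *r*. Assume it lies in the protocol's 3–10 day range for study treatment:

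- *r* = 3: *d* ≤ 4 for TOC on day 7, or *d* ≤ 11 for TOC on day 14.
- *r* = 10: impossible for TOC on day 7; *d* ≤ 4 for TOC on day 14.

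**Path B: failure before 48 hours.** LOS death, or stopping and switching to non-study antibacterials for lack of effect or a related adverse event, meets a failure criterion and also the under-48-hour item. Neither document says which label prevails.

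**Effect on the reported figures.** Inputs: N = 8 (Protocol 8.3; SAP 4.1), and percentages taken over the whole population (SAP 4). Assumed counts, since the documents give no expected rates: 6 uneventful cures, 1 Path A infant, 1 Path B infant.

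| Rating applied | ITT cure at TOC | ITT failures | CE cure, Path A infant kept / dropped |
|---|---|---|---|
| A cure; B failure or unevaluable | 7/8 = 87.5% | 1/8 or 0/8 | 7/7 = 100% / 6/6 = 100% |
| Both failure | 6/8 = 75% | 2/8 = 25% | 6/7 = 85.7% / 6/6 = 100% |
| Both unevaluable | 6/8 = 75% | 0/8 | 6/7 = 85.7% / 6/6 = 100% |

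The shift in ITT cure per Path A infant rated as cure is 1/8 = 12.5 points; two such infants give 2/8 = 25 points. SAP 4 also presents results by term and pre-term group. At the minimum group sizes, one infant is 1/6 = 16.7 points among pre-term and 1/2 = 50 points among term infants.

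The Path B infant is outside CE under either label, because CE requires at least 48 hours of drug (SAP 4.2.2). Whether the Path A infant stays in CE depends on two unstated points: whether antibacterials given for recurrence trigger the CE exclusion for other systemic antibiotics, and whether an unevaluable rating counts as a completed TOC assessment.

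**Microbiology, when no follow-up culture result exists.** Path A rated cure gives presumed eradication, which counts towards the endpoint. Path B moves between presumed persistence and unevaluable; neither counts as eradication, so the mITT eradication rate does not change.

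**The case against.** The best defence is that investigators would treat recurrence as failure anyway. Antibacterials required for persisting or worsening LOS are failure language, the antibiotic item under unevaluable deliberately leaves out treatment for LOS, and only the word for discontinuation fits badly. That is a sensible reading of intent, but the criterion joins discontinuation and further therapy with *and*, and the reasons in Protocol 4.4 do not stretch discontinuation to a completed course.

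One might also say that the LFU relapse definition catches these infants, since its clause on additional antimicrobial therapy is not itself tied to TOC. Even so, it leaves the TOC rating unchanged, and SAP 8.3 tabulates relapse only for the mITT and ME populations. SAP 8.3 does list relapse among the EOT and TOC microbiological outcomes, but this conflicts with Protocol 5.6.3 and has no clinical counterpart.

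Several limits on the impact stand. Moving an infant between failure and unevaluable leaves ITT cure unchanged, because the denominator is the whole population and Protocol 8.4.5 treats an unknown clinical response as non-response. SAP 8.1 tabulates reasons for missing outcomes as well as for failure, and individual data are listed. An LOS death is reported among deaths whatever its clinical label, and in all-cause mortality if it occurs by Day 28. The 48-hour threshold also appears in the CE definition, so a minimum exposure for evaluability may be intended; what is missing is the precedence rule.

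Two stronger conclusions are tempting. A reader might infer that unevaluable is the only label left for a recurrence before TOC; the lead-in to that category, which requires data to be unavailable, does not support this. A reader might also remove unevaluable infants from the denominator and report cure rising from 6/8 = 75% to 6/7 = 86%. No planned analysis uses such a rate; cure is reported in ITT and CE.

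**Conclusion.** The categories in Protocol 5.6.1 have a gap and an overlap, and the SAP closes neither.

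The gap matters more. Re-treatment for LOS after a completed course and before TOC meets no failure criterion, and it literally qualifies as cure if re-treatment is over and the infant is well at TOC. Each such infant overstates ITT cure at TOC by 12.5 points with N = 8, and can add a presumed eradication. This rests on the literal wording, on assumed event counts, and on re-treatment ending before TOC. Where re-treatment is still under way, no label fits, but ITT cure is unaffected provided the infant is not rated a cure.

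The overlap for failures before 48 hours is smaller. It changes the split between failure and unevaluable in the SAP 8.1 table and, without a follow-up culture, one microbiological label. It does not change ITT cure, mITT eradication or CE.

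Because efficacy is secondary and descriptive, no error rate or power is involved. The importance is minor to moderate.

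**What to change.** Add the following to Protocol 5.6.1, or to SAP 8.1 as a derivation rule, before database lock:

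1. Recurrence of LOS, or need for further antibacterial therapy for LOS, after completed study treatment and up to TOC is clinical failure at TOC.
2. Clinical failure at EOT carries forward to TOC. Otherwise an infant who failed, was rescued and is well by TOC meets the cure wording as well as the failure wording.
3. State which label takes precedence when a failure criterion is met with less than 48 hours of study treatment.
4. In the CE definition (Protocol 8.2.2, SAP 4.2.2), state that antibacterials given for failure or recurrence do not trigger the exclusion for other systemic antibiotics. Without this, these failures may leave CE whatever their label, and CE cure tends towards 100%, as in the 6/6 example.

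The cost is a few sentences and some programming. The rules concern classification only; they change no treatment and should need no new assessments, since concomitant medications are already recorded through LFU. The downside is that the reported TOC cure rate may be slightly lower.
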